6.6 HANDLING OF MISSING DATA AND OUTLIERS

No missing data will be imputed in the UPCR, [REDACTED], and urinary protein excretion analyses. Handling of missing PK data will be performed according to the relevant Corporate Procedure.

Missing or incomplete AE dates will be imputed according to BI standards (4). With respect to safety evaluations, it is not planned to impute missing values.

6.7 BASELINE, TIME WINDOWS AND CALCULATED VISITS

The trial consists of a screening period, treatment period, and a follow-up period. Following

the screening period, patients will be randomized (prior to visit 2) to one of the four treatment arms. The treatment period is followed by a 30-day follow-up period which consists of 2 follow-up visits. The 2nd follow-up visit which is also the EoS visit will be completed by telephone except for the eye exams.

For the endpoints collected from 24-hr urine samples, the baseline value will be the average of two (if available) 24-hour urine samples collected before visit 2 (prior to the first treatment).

Baseline for other endpoints will be defined as last available measurement (or sample) prior to first dose..

There will not be any time windows considered or visits calculated.

7. PLANNED ANALYSIS

The individual values of all subjects will be listed, sorted by treatment group, subject number and visit (if visit is applicable in the respective listing). AE listings will be sorted by assigned treatment (see [Section 7.8.1](#), below for details).

For end-of-text tables, the set of summary statistics for non-PK parameters is:

N	number non-missing observations
Mean	arithmetic mean
SD	standard deviation
Min	minimum
Median	median
Max	maximum

For analyte concentrations, as well as for all PK parameters, the following descriptive statistics will additionally be calculated:

CV	arithmetic coefficient of variation
gMean	geometric mean
gCV	geometric coefficient of variation

The data format for descriptive statistics of plasma concentrations will be identical with the data format of the respective concentrations. The descriptive statistics of PK parameters will be calculated using the individual values with the number of decimal places as provided by the evaluation program.

Tabulations of frequencies for categorical data will include all possible categories and will display the number of observations in a category as well as the percentage (%) relative to the respective treatment group. Percentages will be rounded to one decimal place. The category missing will be displayed if and only if there are actually missing values. Percentages will be based on all subjects, in the respective subject set, whether they have non-missing values or not.

7.1 DEMOGRAPHIC AND OTHER BASELINE CHARACTERISTICS

Only descriptive statistics are planned for this section of the report. Demographic parameters collected and to be presented include, but are not limited to, the following:

- Sex (Male, Female)
- Race and ethnicity (as defined in the eCRF)
- Race (Asian/ non-Asian)
- Age [years]
- Age (< Median [years], =>Median [years])
- Height [cm] at baseline
- Weight [kg] (continuous) at baseline
- Body mass index (BMI) [kg/m²] (defined as weight [kg]/(height [cm]/100)²) at baseline
- eGFR [mL/min/1.73m²] at screening: <=45, >45 mL/min/1.73m²
- eGFR [mL/min/1.73m²] at baseline
- UPCR from 24-hour Urine [g/g] at baseline (Baseline UPCR is the average of two, 24-hour urine samples collected before Visit 2)
- UPCR from 24-hour Urine: <3.5[g/g] , => 3.5[g/g]
- Serum Albumin (Screening Visit): <30 [g/L], =>30 [g/L]
- FSGS history: <6 [months], 6 [months] to <2 [years] and => 2 [years]
- SGLT2 Inhibitors Use at baseline (Yes, No)
- Corticosteroid Use at randomization (Yes, No)
- Presence of Monogenic Disease (TRPC6) (Yes, No)

7.2 CONCOMITANT DISEASES AND MEDICATION

Concomitant diseases will be summarized descriptively. The frequency [N (%)] of patients with different concomitant diseases (baseline conditions) will be presented. The concomitant medications taken at baseline and those taken while on treatment will be coded using the World Health Organization (WHO) Drug coding dictionary. These will then be summarized by ATC class 3 and preferred term and listed by patient with each medication taken.

Concomitant non-Drug Therapies will also be summarized descriptively.

7.3 TREATMENT COMPLIANCE

Neither pill counts nor compliance percentages are collected in this trial. However, information is obtained regarding patients who were treatment non-compliant. A by-patient listing for non-compliance will be provided.

7.4 PRIMARY OBJECTIVE ANALYSIS

7.4.1 Primary analysis of the primary endpoint(s)

This is an exploratory trial. No confirmatory testing is performed and hence neither null nor alternative hypotheses are defined. Nominal p-values may be presented. The FAS will be used for the analysis of the primary endpoint.

An exploratory analysis for the primary endpoint, in terms of proportion of patients achieving at least 25% UPCR reduction relative to baseline at week 12 (patients missing the week 12, 24-hr UPCR will be counted as non-responders) will be conducted by providing 95% confidence intervals from each treatment group, via logistic regression utilizing corticosteroid use at randomization (variable CORTIC) and baseline 24-hr UPCR, as covariates. The baseline UPCR will be from the average of two 24-hour urine samples collected before visit 2 (before the first dose). Graphical representations of change in 24-hour UPCR from baseline will also be presented.

The primary estimand of interest is the treatment effect, assuming all subjects remained adherent to the assigned trial medication, and the study protocol using a hypothetical approach, i.e., study drug is taken as directed. This analysis will include all data collected until time of an ICE. For primary analysis, UPCR measurements after ICE will not be included. ICE and the strategies for handling intercurrent events are defined in the CTP section 7.2.2 and [section 6.3](#), above, as follows:

An intercurrent event (ICE) is defined as an event of,

[figure not shown]
- Early discontinuation,
- Lost to follow-up, or
- Death.

The strategies for handling intercurrent events in this trial are as follows:

- (1) Hypothetical estimand: assuming all subjects remained adherent to the assigned trial medication and the study protocol. This strategy will include all data collected until time of an ICE.
- (2) Treatment policy estimand: using all available data including data collected after an ICE.

For this analysis only the Hypothetical estimand will be considered.

In addition, an analysis of covariance (ANCOVA) model (for the UPCR change from baseline at week 12) will be used to see differences across arms, with corticosteroid use at randomization and baseline 24-hr UPCR, as covariates. Dose-response relationship based on reduction in log of UPCR may be explored using a graphical approach.

[figure not shown]

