For visits 3, EoT, and FUP1, one 24-hour urine sample will be collected. Collection should start preferably the day before the respective study visit and end on the day of the visit.

Visit 2 must be rescheduled if at least one of the 24-hour urine sample is not collected. The EoT visit must be rescheduled if the 24-hour urine sample is not collected before the visit. Visits must be rescheduled as soon as possible.

For patients participating in the trial remotely via the DCT model, urine collection containers for all the study visits will be sent to the patient's home, and the urine samples will be shipped to the study site via a courier. If patients live close to the study site, they may also pick up the urine collection containers from the study site and bring the 24-hour urine samples to the study site.

If possible, patients should be reminded (e.g. via telephone) during the screening period and ahead of the applicable visits to collect the 24-hour urine samples.

Collection of 24-hour urine samples may be repeated for logistical reasons (e.g. samples lost or patient could not complete the 24-hour collection) or technical issues (e.g. sample not fit for analysis).

Pregnancy tests

All WOCBP will undergo serum pregnancy test at the screening visit (visit 1). Patients who test positive for the serum pregnancy test will be excluded from the trial. If the patient is a WOCBP, the status of the menstrual cycle should be assessed before the administration of the first dose of trial medication (visit 2): in case of a delayed or missed period, the PI should use their clinical judgement and the results of the pregnancy test at visit 2 to assess the participants pregnancy status and confirm eligibility before intake of trial drug.

Urine pregnancy tests will be done at all study visits starting from visit 2 (except visit 3 and phone visits). If the urine pregnancy test is positive, trial medication will be stopped and a serum pregnancy test will be performed to confirm pregnancy. If the serum pregnancy test is positive, the patient will be discontinued from the trial. EoT visit will be scheduled as soon as possible, and patient should complete the EoS visit. If serum pregnancy is negative, patient may continue in the trial and resume treatment with trial medication. If the urine pregnancy

Clinical Trial Protocol

Proprietary confidential information © 2025 Boehringer Ingelheim International GmbH or one or more of its affiliated companies

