7.2.3 Primary endpoint analyses

An exploratory inferential analysis for the primary endpoint, in terms of proportion of patients achieving at least 25% UPCR reduction relative to baseline at 12 weeks, will be conducted by providing 95% confidence intervals from each treatment group. The primary estimand of interest is the treatment effect assuming all subjects remained adherent to the assigned trial medication and the study protocol using a hypothetical approach, i.e., study drug is taken as directed. This analysis will include all data collected until time of an ICE.

In addition, an analysis of variance (ANOVA) model (for the UPCR change from baseline at week 12) will be used to see difference across arms. Dose-response relationship based on reduction in log of UPCR may be explored using graphical approach.

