6.4 SUBJECT SETS ANALYSED

Subject sets will be used, as defined in the CTP Section 7.2.1.

The following analysis sets will be defined for statistical analyses:

- Entered Set (ES): This patient set includes all patients who signed informed consent. The ES will be used for the analysis of patient disposition.
- Randomized Set (RS): This patient set includes all patients who signed the informed consent form and were also randomised, regardless whether the patient was treated with trial medication or not.
- Treated Set (TS): This patient set includes all patients who received at least one dose of trial medication. The TS is used for safety and treatment exposure.
- Full Analysis Set (FAS): This patient set includes all patients who were randomized and treated with evaluable measurements of 24-hr UPCR at baseline and at least one 24-hr UPCR measurement after the first dose. The FAS is the main analysis set for the analysis of efficacy.
- Per Protocol (PPS): All patients who were randomized and completed treatment with evaluable measurements of primary endpoint at both baseline and end of treatment visits within the residual period (5 days). The PPS is the analysis set used in the Sensitivity analysis.
- Pharmacokinetic Analysis Set (PKS): This patient set includes all patients in the TS who provide at least one PK endpoint that was not excluded due to protocol violation relevant to the evaluation of PK or due to PK non-evaluability.
- ECG Pharmacokinetic Concentration Set (ECGPCS): This patient set includes all subjects from the TS who provided at least one pair of a valid drug plasma concentration and a corresponding (i.e. time-matched) ECG endpoint to be used in the exposure-response analysis e.g. concentration-QT plots. For placebo subjects, the plasma concentration is set to zero and hence always considered as valid. The decision whether a time deviation between PK blood sampling and ECG recording is acceptable (and thus whether the pair of values were used) will be made no later than at the RPM before database lock.

If a patient receives incorrect medication for the entire treatment period, efficacy will be analysed as randomized and safety will be analysed as treated. If a patient receives incorrect medication for part of the treatment period, the primary analysis of the primary efficacy endpoint will be performed on the randomized set following the intention-to-treat principle. Such cases will be discussed in the RPM, if needed.

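### SAP 7.4.1 scores a missing week-12 UPCR as non-response under a full-adherence estimand, so an arm's responder rate can be understated for that estimand

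*SAP*

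**What the plan says.** Protocol 7.2.3 sets the target: "The primary estimand of interest is the treatment effect assuming all subjects remained adherent to the assigned trial medication and the study protocol". SAP 7.4.1 repeats it and adds "For this analysis only the Hypothetical estimand will be considered". Intercurrent events are early discontinuation, loss to follow-up and death (Protocol 7.2.2, SAP 6.3).

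SAP 7.4.1 also gives two data rules for the same analysis:

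- "For primary analysis, UPCR measurements after ICE will not be included"
- "patients missing the week 12, 24-hr UPCR will be counted as non-responders"

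The analysis uses the full analysis set (FAS). SAP 6.4 admits patients who were "treated with evaluable measurements of 24-hr UPCR at baseline and at least one 24-hr UPCR measurement after the first dose". Flow Chart A schedules one 24-hour urine before visit 3 (day 4), so that sample alone is enough for entry.

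Three other places bear on the point. SAP 6.6 and Protocol 7.3 rule out imputation in the UPCR analyses. Protocol 2.1.1 describes the primary comparison as on-treatment. SAP 6.7 says "There will not be any time windows considered or visits calculated".

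**The concern.** A hypothetical estimand asks what the response rate would have been had everyone kept taking the assigned drug. The SAP's rule answers a different question. Once post-event values are dropped, a patient who discontinues before week 12 has no usable week-12 value and is scored as a failure. Either the event itself counts as failure, which is a composite strategy, or the plan assumes without saying so that the patient would not have responded under adherence. For a week-12 value missing without an intercurrent event, the rule is a worst-case missing-data assumption.

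The responder rates are the main readout of a proof-of-principle trial with 15 patients planned per arm. They would be reported as full-adherence rates while partly reflecting drop-out. If drop-out differs by dose, the apparent dose ordering would mix efficacy with retention.

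**Working it through.** **Who is affected.** A patient with a baseline UPCR and a visit 3 urine who then stops treatment is in the FAS. Any later UPCR is excluded as post-event, so the week-12 value is missing and the patient stays in the denominator as a non-responder. Values missing without an event should be few: Protocol 6.1 says "The EoT visit must be rescheduled if the 24-hour urine sample is not collected before the visit" and "Collection of 24-hour urine samples may be repeated for logistical reasons".

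**Formula.** Let *p* be an arm's full-adherence response rate, *m* the share of its FAS patients without a usable week-12 value, and *f × p* the rate at which those patients would have responded under adherence.

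- Scored rate = *p* − *m* × *f* × *p* = *p* × (1 − *f* × *m*)
- Shortfall = *f* × *m* × *p*. It is never negative, and with *m* and *p* above zero it vanishes only if *f* = 0.

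**Inputs.** Protocol 7.5 gives *p* = 0.40 for 80 mg and 0.09 for placebo. The documents give neither *m* nor *f*, so the values below are assumptions. The sums use crude proportions and ignore the covariates in the SAP's logistic model.

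**If the planning rates are full-adherence rates** (true difference 0.40 − 0.09 = 31 points):

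| Missing | *f* = 1 | *f* = 0.5 | *f* = 0 |
|---|---|---|---|
| 10% in both arms | 0.40×0.90 − 0.09×0.90 = 27.9 | 0.40×0.95 − 0.09×0.95 = 29.45 | 31 |
| 20% in both arms | 0.40×0.80 − 0.09×0.80 = 24.8 | 0.40×0.90 − 0.09×0.90 = 27.9 | 31 |
| 20% on placebo only | 0.40 − 0.09×0.80 = 32.8 | 0.40 − 0.09×0.90 = 31.9 | 31 |

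**If the planning rates already count missing as failure** (*f* = 1), the reported difference is 31 points and the full-adherence difference is 0.40/(1 − *m*₈₀) − 0.09/(1 − *m*₀), where *m*₈₀ and *m*₀ are the missing shares on 80 mg and placebo:

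- 10% in both arms: 0.4444 − 0.1000 = 34.4 points
- 20% in both arms: 0.5000 − 0.1125 = 38.75 points
- 20% on placebo only: 0.4000 − 0.1125 = 28.75 points

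**Direction.** A single arm's rate can only be understated. The contrast with placebo can move either way. With the same *f* in both arms it is overstated only when *m*₀ × 0.09 exceeds *m*₈₀ × 0.40, that is, when the missing share on placebo is more than 0.40/0.09 = 4.4 times that on 80 mg.

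**Per patient.** At 15 per arm one patient is 1/15 = 6.7 points of the observed rate. The expected understatement at a 40% would-be response is 0.40/15 = 2.7 points for one missing patient and 5.3 for two. On placebo it is 0.09/15 = 0.6 and 1.2.

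**The plan's own probability.** The 73.4% in Protocol 7.5 is not an input here. Exact enumeration with four sampled arms of 15 gives 80.7%. Two variants that the protocol does not state come close: placebo fixed at 9% gives 72.7%, and 13 per arm gives 72.2%. Nothing in this point depends on which was used.

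**The case against.** Scoring missing as failure is a familiar convention and is stated openly. It could be read as a conservative estimator of the hypothetical quantity, in which case one sentence stating the assumption would do. Neither Protocol 7.2.2 nor SAP 6.3 lists a composite strategy, so relabelling alters a named estimand. The number of patients affected may be small. Discontinuers have an end-of-treatment visit as soon as possible, and no text dates the intercurrent event or says whether that urine counts as week 12. The shift is also modest beside sampling error: the exact 95% interval for 6 of 15 runs from 16% to 68%. The trial tests no hypothesis. A per-protocol sensitivity analysis and a treatment-policy supplement are planned, and redacted SAP text may hold more.

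The unknown size, the exploratory setting and the open status of the early end-of-treatment urine all stand, and they limit how serious the point is. The conservative reading does not remove it: the scored rate equals the stated estimand only if no missing patient would have responded. The ANCOVA, per-protocol and treatment-policy analyses are useful checks but do not change what the primary rates measure.

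**Conclusion.** The concern holds. SAP 7.4.1 pairs a full-adherence estimand with a scoring rule that does not estimate it, and no visible text reconciles the two. Each arm's scored rate is at or below its full-adherence rate, by the share missing times the response rate those patients would have had.

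The size cannot be fixed from the documents, because no drop-out rate is given and the planning rates are not said to be full-adherence rates. Across the illustrations, a true 31-point difference is scored as 24.8 to 32.8 points, and a reported 31 corresponds to a true 28.75 to 38.75. Some of these cross the 25-point goal in Protocol 7.5, but that goal is a planning statement and not a test. The consequence is a responder rate or dose comparison that may be misread. It should be fixed, and it does not threaten a confirmatory conclusion because none is planned.

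**What to change.** Before unblinding, keep the non-responder rule and make its label agree with it:

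- In SAP 7.4.1, name the analysis a composite estimand in which discontinuation, loss to follow-up or death before the week-12 urine is non-response. Do not report these rates as full-adherence effects.
- State separately that a week-12 value missing without an intercurrent event is missing data scored as non-response, and note this as an exception to SAP 6.6.
- State when the intercurrent event is dated and how an early discontinuer's end-of-treatment urine is classed against it.
- Tabulate missing week-12 values by arm and reason. SAP 7 already provides all-subject denominators and a missing category, so only the reason is new.
- Align the on-treatment wording of Protocol 2.1.1, and record the departure from Protocol 7.2.3 in SAP section 4, unless it is already in the part not visible (the visible list starts at item 2).

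A model-based hypothetical analysis, such as multiple imputation of log UPCR followed by dichotomising, is optional and suits a sensitivity analysis only. For early leavers it would rest on a single day-4 value at about 15 patients per arm.

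The cost is SAP wording and one small table, with no new data. The real price is that the named primary estimand changes from the protocol's, and that must be documented.

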6.3 INTERCURRENT EVENTS

An intercurrent event (ICE) is defined as an event of early discontinuation, lost to follow-up, or death.

The strategies for handling intercurrent events in this trial are as follows:

- Hypothetical estimand: assuming all subjects remained adherent to the assigned trial medication and the study protocol. This strategy will include all data collected until time of an ICE.
- Treatment policy estimand: using all available data including data collected after an ICE.

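### The supplementary week-12 ANCOVA of UPCR leaves out patients with an early intercurrent event; a two-visit repeated-measures model would use their day-4 urine, for a modest gain

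*SAP*

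**What the plan says.** SAP 7.4.1 places the primary responder analysis under the hypothetical estimand: "This analysis will include all data collected until time of an ICE", and "UPCR measurements after ICE will not be included". SAP 6.3 and Protocol 7.2.2 set out the same strategy for the trial as a whole. SAP 6.3 adds: "An intercurrent event (ICE) is defined as an event of early discontinuation, lost to follow-up, or death". Protocol 2.1.1 describes the primary comparison as on-treatment, using data collected before early discontinuation or loss to follow-up.

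For continuous UPCR, 7.4.1 adds: "analysis of covariance (ANCOVA) model (for the UPCR change from baseline at week 12) will be used to see differences across arms". The covariates are corticosteroid use and baseline 24-hour UPCR. SAP 6.6 states: "No missing data will be imputed in the UPCR". The FAS asks only for a baseline value and "at least one 24-hr UPCR measurement after the first dose". In the responder model, "patients missing the week 12, 24-hr UPCR will be counted as non-responders".

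On the data available, Protocol 6.1 states: "For visits 3, EoT, and FUP1, one 24-hour urine sample will be collected". Visit 3 is day 4 (window +3 days), the end-of-treatment (EoT) visit is week 12 and FUP1 is week 13. Patients who discontinue early have their EoT visit brought forward.

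**The concern.** A patient who gives a visit 3 urine and then stops before week 12 belongs to the FAS and has a valid on-treatment UPCR. The ANCOVA has no week-12 value for that patient and none is imputed, so the patient is not in the model. The FAS is named as the main efficacy set, but the ANCOVA is in effect an analysis of completers, and it does not use all pre-ICE data as the stated strategy requires.

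At stake is the continuous estimate of differences across arms. With 15 patients per arm, each dropped patient matters. If stopping differs by dose and is related to how proteinuria is running, completers on that dose will look better than the whole arm would have done under full adherence.

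**Working it through.** **Step 1. Which patients and which urines.** For a patient with an ICE between day 4 and week 12:

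| 24-hour urine | Timing relative to ICE | Week-12 ANCOVA | Two-visit model |
|---|---|---|---|
| Visit 3 (day 4) | before | not used | used |
| EoT, brought forward | after | excluded | excluded |
| FUP1 | after | excluded | excluded |

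So one urine per such patient is recoverable. A patient whose only post-dose urine comes after the ICE is unused in both models. In the primary logistic model all of these patients enter as non-responders.

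SAP 6.7 applies no time windows. Nothing there says in terms that a brought-forward EoT urine is not a week-12 value; that follows only from the post-ICE exclusion.

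**Step 2. Precision.** The plan gives no ICE rate, SD or day-4 to week-12 correlation, so there is no figure of its own to reproduce here. (The 73.4% in Protocol 7.5 concerns responder rates and does not enter.) Assume that a share d of each arm lacks week 12, that visit 3 is complete, and that the correlation given covariates is ρ. If stopping is random,

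variance ratio (repeated measures / ANCOVA) = 1 − ρ²d; effective n per arm = 15(1 − d) / (1 − ρ²d).

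| d | ρ | Variance ratio | n, ANCOVA | n, repeated measures |
|---|---|---|---|---|
| 1/15 | 0.3 | 1 − 0.09 × 0.067 = 0.994 | 14.0 | 14.1 |
| 2/15 | 0.5 | 1 − 0.25 × 0.133 = 0.967 | 13.0 | 13.4 |
| 0.20 | 0.3 | 1 − 0.09 × 0.20 = 0.982 | 12.0 | 12.2 |
| 0.20 | 0.5 | 1 − 0.25 × 0.20 = 0.950 | 12.0 | 12.6 |
| 0.20 | 0.7 | 1 − 0.49 × 0.20 = 0.902 | 12.0 | 13.3 |

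The saving is about 1 to 10% of variance. Simulation with 15 per arm agreed: 0.941 at d = 0.20, ρ = 0.5, and 0.883 at d = 0.20, ρ = 0.7.

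**Step 3. Bias, by simulation.** Effects in SD units come from the responder rates in Protocol 7.5: z(0.40) − z(0.09) = 1.09, z(0.30) − z(0.09) = 0.82 and z(0.20) − z(0.09) = 0.50. Assumed, and not in the documents: 40% of the effect present at day 4; correlation 0.6; ICE rates of 5/10/20/30% from placebo to 80 mg; odds of an ICE doubling per SD of higher UPCR. Results are for 80 mg minus placebo, true effect −1.09 SD. A negative bias favours 80 mg.

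| Stopping depends on | ANCOVA bias (SD) | Repeated-measures bias (SD) |
|---|---|---|
| day-4 UPCR | −0.098 | 0.000 |
| day-4 UPCR, ICE 5/10/15/20% | −0.057 | −0.003 |
| midpoint of day-4 and week-12 UPCR | −0.124 | −0.048 |
| week-12 UPCR | −0.151 | −0.098 |
| nothing related to UPCR | no material bias | no material bias |

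In the first row the standard errors are 0.410 and 0.399 SD. The bias is 0.098 / 1.09 = 9% of the effect, and 0.057 / 1.09 = 5% at the lower ICE rates. Raising the correlation to 0.8 gave an ANCOVA bias of 0.12 to 0.14 SD across runs. In the last-but-one row 0.098 / 0.151 = 65% of the bias remains. Root mean squared error falls from 0.417 to 0.397 in the first setting (about 5%) and from 0.386 to 0.375 at the lower ICE rates (about 3%).

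**Step 4. A second set of assumptions.** Log scale, SD 0.5, true effect −0.35, stopping related to day-4 response in the 80 mg arm only (odds ratio 2.7 per SD), ICE 10 to 20%, ρ from 0.3 to 0.7. The ANCOVA was biased towards 80 mg by 0.02 to 0.07 log units; the repeated-measures estimate was within 0.01 of the truth.

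**The case against.** The case against acting is substantial, and much of it limits the point.

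- **A reader might infer that these patients contribute nothing to the trial's efficacy analysis.** The documents do not support that. They count as non-responders in the primary logistic model. In 7.4.1 the sentence on including data up to the ICE is attached to that analysis, and the ANCOVA follows as an addition. What stands is that SAP 6.3 and Protocol 7.2.2 give the hypothetical strategy for the trial generally, and that the ANCOVA is the visible model meant to show differences across arms.
- **A reader might infer that QT-related stopping at 80 mg biases the ANCOVA.** Protocol 1.2 does report possible dose-dependent QT prolongation from 80 mg upwards. But none of the discontinuation criteria in Protocol 3.3.4.1 is triggered by UPCR. Dose-related stopping that is unrelated to UPCR costs precision and causes no bias.
- **A reader might infer that repeated measures removes the bias altogether.** It does so only when stopping depends on covariates and day-4 UPCR alone. No 24-hour urine is taken between day 4 and week 12, so stopping driven by later proteinuria is only partly corrected.
- **The size is small and assumed.** This is correct: 0.10 SD against a standard error of 0.41 SD, in an exploratory trial without hypotheses.
- **Parts of the SAP are redacted.** It mentions MCP-Mod and a per-protocol sensitivity analysis whose details are not visible. Another model using visit 3 may exist, so the point covers the visible text only.

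Against this, the two models give the same answer when data are complete, and in no setting examined did the repeated-measures model do materially worse.

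**Conclusion.** The point holds for the supplementary ANCOVA. As visible, it is a complete-case, week-12 model that omits FAS patients with a visit 3 urine and an earlier ICE, contrary to the stated strategy of using data up to the ICE. The recoverable information is one day-4 urine per such patient.

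The gain from using it is modest: about 1 to 10% of variance with up to 20% ICE and ρ between 0.3 and 0.7, and about 0.05 to 0.10 SD less bias if stopping depends on early UPCR. The correction is partial if stopping depends on later UPCR, and there is nothing to correct if it is unrelated to UPCR. ICE rates, correlations and the stopping mechanism are assumptions throughout. The change is still worth making because it needs no new data and brings the model closer to the estimand.

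**What to change.** In SAP 7.4.1, estimate the week-12 difference across arms with a mixed model for repeated measures on log 24-hour UPCR at visit 3 and week 12, using pre-ICE values only. Include arm-by-visit, log-baseline-by-visit and corticosteroid-by-visit terms and an unstructured covariance. Report dose-minus-placebo contrasts at week 12 with 95% confidence intervals. Keep the ANCOVA as a completers' check.

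In SAP 6.7, state that an EoT urine taken after early discontinuation is not analysed as week 12. State the missing-at-random assumption, and that the only post-baseline value it conditions on for patients who stop early is day 4.

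Before editing, the sponsor should confirm that no redacted section already specifies such a model.

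Cost: SAP wording and a few lines of code. The visit 3 urine is already collected. The downside is minor extra analysis work and reliance on an assumption that the data cannot verify.
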